9 TOXICITY MANAGEMENT

9.1 Dose Limiting Toxicity

9.1.1 Reporting a DLT

A dose limiting toxicity is a toxicity that is considered related to M6620 (Berzosertib) or the interaction between M6620 (Berzosertib) and radiotherapy or chemoradiotherapy. **Dose limiting toxicities should be reported within 24 hours of the site becoming aware using the SAE form and scan and email as a PDF attachment to [contact] and send an email notification to [contact].** For management of M6620 (Berzosertib) toxicities see section 9.3. Chemotherapy and radiotherapy toxicities should be managed as per standard practice.

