9.1.2 Definition of a DLT

Stage A1

DLTs will be defined as per NCI CTCAE v4.03 and include:

- Absolute neutrophil count (ANC) $<0.5 \times 10^9/L$ for >7 days
- Febrile neutropenia (fever of unknown origin without clinically or microbiologically documented infection) (ANC $<1.0 \times 10^9/L$, fever $\geq 38.5^\circ C$) lasting >3 days
- Infection (documented clinically or microbiologically) with Grade 3 or 4 neutropenia (absolute neutrophil count $<1.0 \times 10^9/L$)
- Platelets $<25 \times 10^9/L$
- Clinically significant bleeding attributed to grade 3 thrombocytopenia or requiring platelet transfusion
- Grade ≥ 3 oesophagitis onset within 2 weeks of starting radiotherapy
- Grade ≥ 3 pneumonitis onset within 3 months of starting radiotherapy
- Grade ≥ 3 nausea or vomiting not controlled by optimal outpatient anti-emetic treatment
- Grade ≥ 3 diarrhoea despite optimal outpatient anti-diarrhoeal medication use
- Other grade 3 \geq effects thought to be directly treatment related to the combination of M6620 (Berzosertib) with radiotherapy
- Any toxicity causing a delay of radiotherapy completion by greater than one week
- Missing 2 consecutive doses of M6620 (Berzosertib) within a cycle due to Grade ≥ 3 toxicity
- A delay of any of the 3 treatments of 7 days or more within a cycle due to treatment related toxicity
- An elevation of ALT or AST $>5 \times ULN$ lasting 8 days or more
- A concurrent elevation of ALT or AST $>3 \times ULN$ and total bilirubin $>2 \times ULN$ in whom there is no evidence of biliary obstruction or other causes that can reasonably explain the concurrent elevation
- Death due to drug related complications
- Cardiac:
 - QTc prolongation (any QTc interval ≥ 500 msec or any change in QTc interval ≥ 60 msec from baseline) on ECG, unless related to an electrolyte abnormality and prolongation resolves with correction of electrolyte abnormality

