 - Any of the following (CTCAE criteria): Grade 2 or greater ventricular arrhythmia (second or third degree AV block), severe sustained/symptomatic sinus bradycardia less than 45 beats per minute (bpm) or sinus tachycardia >120 bpm not due to other causes (e.g., fever), persistent supraventricular arrhythmia (e.g., uncontrolled/new atrial fibrillation, flutter, atrioventricular nodal tachycardia, etc.) lasting more than 24 hours, ventricular tachycardia defined as >9 beats in a row or any length of torsades de pointes (polymorphic ventricular tachycardia with long QTc), or unexplained recurrent syncope
 - Symptoms suggestive of congestive heart failure with confirmed Ejection Fraction (EF) $<40\%$ (by 2D-echocardiogram or Multiple Gated Acquisition [MUGA] scan)
 - Troponin T: level which is consistent with myocardial infarction

Stage A2

DLTs will be defined as per NCI CTCAE v4.03 and include:

- Absolute neutrophil count (ANC) $<0.5 \times 10^9/L$ for >7 days
- Febrile neutropenia (fever of unknown origin without clinically or microbiologically documented infection) (ANC $<1.0 \times 10^9/L$, fever $\geq 38.5^\circ C$) lasting >3 days

- Infection (documented clinically or microbiologically) with Grade 3 or 4 neutropenia (absolute neutrophil count $<1.0 \times 10^9/L$)
- Platelets $<25 \times 10^9/L$
- Clinically significant bleeding attributed to grade 3 thrombocytopenia or requiring platelet transfusion
- Grade ≥ 3 nausea or vomiting not controlled by optimal outpatient anti-emetic treatment
- Grade ≥ 3 diarrhoea despite optimal outpatient anti-diarrhoeal medication use
- Other grade ≥ 3 effects thought to be directly treatment related to the combination of M6620 (Berzosertib) with chemotherapy
- Missing 2 consecutive doses of M6620 (Berzosertib) within a cycle due to Grade ≥ 3 toxicity
- A delay of any of the 3 treatments of 7 days or more within a cycle due to treatment related toxicity
- An elevation of ALT or AST $>5 \times ULN$ lasting 8 days or more
- A concurrent elevation of ALT or AST $>3 \times ULN$ and total bilirubin $>2 \times ULN$ in whom there is no evidence of biliary obstruction or other causes that can reasonably explain the concurrent elevation
- Death due to drug related complications
- Cardiac:
 - QTc prolongation (any QTc interval ≥ 500 msec or any change in QTc interval ≥ 60 msec from baseline) on ECG, unless related to an electrolyte abnormality and prolongation resolves with correction of electrolyte abnormality

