9.3.2 Toxicities associated with M6620 (Berzosertib)

Acute hypersensitivity reactions are a toxicity of M6620 (Berzosertib). Serious acute hypersensitivity reactions have occurred during the second M6620 (Berzosertib) infusion in approximately 5% of subjects administered M6620 (Berzosertib) and should be reported as a Serious adverse reaction (see section 8.4 for management of hypersensitivity reactions). In at least one sixth of patient reactions at the site of infusion were noted including erythema, swelling, pruritus. The most common toxicities reported in patients who have received M6620 (Berzosertib) are: fatigue, abdominal pain, diarrhoea, nausea and vomiting, decreased appetite, cough, headache and fever. Almost all instances of these toxicities occurred in patients who were also receiving chemotherapy in combination with M6620 (Berzosertib). M6620 (Berzosertib) in combination with chemotherapy may exacerbate the risks associated with the chemotherapy. The most frequently noted grade ≥ 2 laboratory abnormalities observed (in combination with chemotherapy) are neutropenia, low lymphocytes, low haemoglobin and elevated ALT/AST. M6620 (Berzosertib) absorbs UV-visible radiation spectrum and is widely distributed including to the skin, so subjects should be cautioned to minimise exposure to the sun and other sources of visible and UV radiation and to take protective measures when necessary. Full range of toxicities can be found in the M6620 (Berzosertib) IB.

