14.5 Summary of trial safety reporting requirements

Please note all standard treatment toxicities **must be** reported because the TiTE-CRM trial design is based on an expected frequency of standard treatment toxicities plus M6620 (Berzosertib) related toxicities.

Event	DLT	SAE ¹	AE/SAE	AE/SAE
AE/SAE defined as Dose limiting toxicity (DLT) defined as per NCI CTCAE v4.03		Email reporting form within 24 hours	Report in AE CRF	Non reportable
Absolute neutrophil count (ANC) $<0.5 \times 10^9/L$ for >7 days	x	x	x	
Febrile Neutropenia (ANC $<1.0 \times 10^9/L$, fever $\geq 38.5^{\circ}C$) for >3 days	x	x	x	
Infection (documented clinically or microbiologically) with Grade 3 or 4 neutropenia (absolute neutrophil count $<1.0 \times 10^9/L$)	x	x	x	
Platelets $<25 \times 10^9/L$ (Grade ≥ 4)	x	x	x	
Clinically significant bleeding attributed to grade 3 thrombocytopenia or requiring platelet transfusion	x	x	x	
Grade ≥ 3 oesophagitis onset during induction chemotherapy or within 2 weeks of starting radiotherapy	x	x	x	
Grade ≥ 3 pneumonitis onset within 3 months of starting radiotherapy	x	x	x	
Grade ≥ 3 elevation of ALT or AST lasting 8 days or more	x	x	x	
A concurrent elevation of ALT or AST $>3 \times$ ULN and total bilirubin $>2 \times$ ULN in whom there is no evidence of biliary obstruction or other causes that can reasonably explain the concurrent elevation	x	x	x	
Grade ≥ 3 nausea or vomiting not controlled by optimal outpatient anti-emetic treatment	x	x	x	
Grade ≥ 3 diarrhoea despite optimal outpatient anti-diarrhoeal medication use	x	x	x	
Other grade ≥ 3 effects thought to be directly treatment related to the combination of M6620 (Berzosertib) with radiotherapy or chemotherapy	x	x	x	
Any toxicity causing a delay of radiotherapy completion by greater than one week for Stage A	x	x	x	
Any toxicity causing radiotherapy delivery delay by ≥ 3 consecutive fractions for stage B	x	x	x	
Missing 2 consecutive doses of M6620 (Berzosertib) within a cycle due to Grade ≥ 3 toxicity	x	x	x	
Death due to drug related complications	x	x	x	
Cardiac toxicity: see section 9.1.2	x	x	x	
A delay of any of the 3 treatments of 7 days or more within a cycle due to treatment related toxicity	x	x	x	
AE/SAE defined as late DLT (onset 6 weeks after completion of radiotherapy) as per RTOG/EORTC late toxicity and Mellow Dysphagia score (Appendix C, D)				
Grade ≥ 3 lung and heart toxicity – onset 6 weeks after completion of radiotherapy	x	x	x	

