Grade 3 oesophageal toxicity with an increase in Mellow score by ≥ 2 since baseline (need to exclude disease progression on CT and/or endoscopy and biopsy) - onset 6 weeks after completion of radiotherapy	x	x	x	

Grade 4 oesophageal toxicity - onset 6 weeks after completion of radiotherapy	X	X	X	
Medically important events in the context of this trial (considered dose limiting and possibly related to M6620 (Berzosertib) combined with Radiotherapy +/- chemotherapy by the TMG)		Email reporting form within 24 hours	Report in AE CRF	Non reportable
Any AE not listed above that is grade ≥ 3		X	X	
AE considered more severe than expected		X	X	
AE Grade <3 that is unexpected and thought to be directly treatment related to the combination of M6620 (Berzosertib) with radiotherapy +/- chemotherapy		X	X	
AE resulting in withdrawal		X	X	
Any late grade ≥ 3 toxicities – onset 6 weeks after completion of radiotherapy		X	X	
Any late grade 2 toxicities – onset 6 weeks after completion of radiotherapy			X	
Acute Hypersensitivity reaction		X	X	
Expected non-dose limiting toxicities		Email reporting form within 24 hours	Report in AE CRF	Non reportable
Anaemia		If grade ≥ 4	X	
Abdominal pain		If grade ≥ 4	X	
Cough			X	
Decreased appetite		If grade ≥ 4	X	
Elevated ALT/AST lasting less than 8 days		If grade ≥ 4	X	
Fatigue		If grade ≥ 4	X	
Headache			X	
Low lymphocytes			X	
Infusion-related site reaction		If grade ≥ 3	X	
Skin rash/discolouration related to sun exposure		If grade ≥ 4	X	
Grade <3 nausea or vomiting			X	
All other AEs, abnormal assessments or laboratory results		Email reporting form within 24 hours	Report in AE CRF	Non reportable
All other AEs, assessments, abnormal laboratory results, if clinically significant		If grade ≥ 3	X	
AE is life-threatening		X	X	
AE requires in-patient hospitalisation or prolongs existing inpatient hospitalisation		X	X	
AE results in persistent or significant incapacity or disability		X	X	
AE is a congenital anomaly or birth defect		X	X	
AE is any other medically important event		X	X	
Disease progression and resultant death		Email reporting form within 24 hours	Report in AE CRF	Non reportable
Hospitalisation (for progression or procedures planned prior to informed consent)				X

Clinical symptoms of progression				x
Death		Possibly related directly to M6620 (Berzosertib) or the combination of M6620 (Berzosertib) + radiotherapy +/- chemotherapy	Report death and reason on death notification CRF	

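### A combination-related grade 3 event such as fatigue or anaemia is a DLT under Protocol 9.1.2 but is listed as not dose limiting in Protocol 14.5, and nothing says which applies

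*Protocol*

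**What the plan says.** **The DLT rule.** Protocol 9.1.2 ends each stage's list of specific DLTs with a general item. In Stage A1 it covers grade 3 or worse "effects thought to be directly treatment related to the combination of M6620 (Berzosertib) with radiotherapy", and in Stage A2 grade 3 or worse "effects thought to be directly treatment related to the combination of M6620 (Berzosertib) with chemotherapy". Stage B has the equivalent item for chemotherapy or radiotherapy. No named event is exempted. The DLT block of the table in Protocol 14.5 repeats the item for grade 3 or worse "effects thought to be directly treatment related to the combination of M6620 (Berzosertib) with radiotherapy or chemotherapy", with ticks for DLT, SAE form and AE CRF.

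**The later rows of the same table.**
- Under "Expected non-dose limiting toxicities", anaemia, abdominal pain, decreased appetite and fatigue have no DLT tick and need an SAE form only from grade 4.
- Low lymphocytes, cough and headache, in the same block, have no DLT tick and no SAE entry at any grade.
- The nausea and vomiting row of that block is limited to below grade 3. The seven rows above have no such limit, and none carries an attribution condition.
- Just before that block, a row that begins "Any AE not listed above that is grade" 3 or higher asks for an SAE form but gives no DLT tick.

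**The reporting route.** Protocol 9.1.1: "Dose limiting toxicities should be reported within 24 hours of the site becoming aware using the SAE form".

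**How common the events are.** Protocol 9.3.2: "The most common toxicities reported in patients who have received M6620 (Berzosertib) are: fatigue, abdominal pain, diarrhoea, nausea and vomiting, decreased appetite", then cough, headache and fever. It also names low lymphocytes and low haemoglobin among the most frequent laboratory abnormalities of grade 2 or worse.

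**The concern.** Whether a patient had a DLT is the only toxicity outcome in the TiTE-CRM likelihood. Take a grade 3 fatigue that the investigator attributes to the combination. Under 9.1.2 the outcome is y = 1 and the event goes on an SAE form within 24 hours. Under the later block of 14.5 it is not dose limiting and goes only on the AE CRF. The third row would send an SAE form without marking a DLT. The conflict therefore remains after attribution has been settled.

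If sites follow different rows, the fitted curve mixes two endpoints. If all follow the later block, the DLT rate is understated relative to 9.1.2. None of the four sensitivity analyses in SAP 7.4 would reveal either, because they vary weights, dose received and pending outcomes, not the DLT definition.

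**Working it through.** **Inputs (SAP 3.1.1, 3.3 and Table 1).** Curve g_k(α) = s_k^exp(α), with α ~ N(0, 1.158²). Skeleton s for A1: 0.12, 0.15, 0.18, 0.20, 0.22, 0.25. For A2: 0.17, 0.20, 0.25, 0.30. Targets 0.25 and 0.30. Chosen schedule: closest to but not above the target on the posterior mean. Safety stop: P(toxicity at lowest schedule > target) > 0.95.

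**1. Reproduce the plan's figures.** SAP 3.6 gives 18 patients (10, 20) for A1 and 16 (11, 20) for A2. Simulating 1,000 trials gave 17.3 (10–20) and 15.9 (11–20). Assumptions: true rates equal to the skeleton, uniform DLT times. The rule that 3/3 DLTs is too toxic also follows: P = 0.984 (A1) and 0.975 (A2).

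**2. First cohort of three on schedule 1.** With weight 1 for every patient (assumption: full window and full planned M6620), L(α) = g_1^y (1 − g_1)^(3−y), and the estimate is E[g_1(α) | y].

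| | 0/3 DLTs | 1/3 DLTs | Target |
|---|---|---|---|
| A1 | 0.078 | 0.314 | 0.25 |
| A2 | 0.090 | 0.330 | 0.30 |

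With 0/3, every schedule is below target (top-schedule estimate 0.146 in A1, 0.155 in A2), so the next patient may go to schedule 2. With 1/3, even the lowest schedule is above target and allocation stays there. One re-scored patient makes the difference.

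**3. Final result, full follow-up, same patients scored both ways.** All placements of the DLTs were tried.

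| Stage, patients per schedule | DLTs without the listed events | Selected | DLTs with them | Selected |
|---|---|---|---|---|
| A2, 3/3/3/6 | 3 | 3 or 4 | 6 | none |
| A2, 3/1/1/6 | 2 | 4 | 4 | 1 or none |
| A2, 3/1/1/6 | 2 | 4 | 5 | none |
| A1, 3/1/1/1/1/10 | 3 | 5 or 6 | 6 | 1 or none |
| A1, 3/1/1/1/1/10 | 3 | 5 or 6 | 7 | none |

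The shift from top schedule to none takes 2–3 re-scored patients in A2 (4 − 2, 5 − 2, 6 − 3) and 3–4 in A1 (6 − 3, 7 − 3).

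**4. None is not the safety stop.** The 0.95 threshold is reached at about 9 DLTs in 15 patients (A2; P 0.93 to 0.97 by placement) or 10 in 17 (A1; P 0.95 to 0.98). Below that, SAP 3.2 keeps assigning the lowest schedule.

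**5. Illustrative frequencies.** The rate of related grade 3 or worse listed events is not in the documents; 5% to 30% is assumed. Paired simulation, 500 trials per setting, other DLTs at skeleton rates:

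| Extra event rate | 5% | 10% | 20% | 30% |
|---|---|---|---|---|
| A1 top schedule selected (48% if not counted) | 32% | 19% | 5% | 1% |
| A1 none selected (10% if not counted) | 24% | 35% | 66% | 86% |
| A1 top to none, same trial | 3% | 7% | 26% | 39% |
| A2 top schedule selected (52% if not counted) | 40% | 25% | 9% | 3% |
| A2 none selected (8% if not counted) | 16% | 28% | 63% | 87% |
| A2 top to none, same trial | 1% | 6% | 25% | 41% |

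At 5%, some change of selected schedule occurred in 34% (A1) and 29% (A2) of trials. With other DLTs at half the skeleton, these were 21% and 15%. Stage B cannot be computed, because SAP Table 1 omits its design features.

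**The case against.** The strongest reply is that a governing list exists. Every stage's primary endpoint points to 9.1.2, and 14.5 is a reporting summary whose own DLT block ticks a related grade 3 event before the reader reaches the later rows. On that reading the later block covers only events not attributed to the combination. This is the more natural reading, and it means that 14.5 does not simply score these events as y = 0. It stands as a reason to expect many sites to score correctly. It does not settle the matter: the later rows carry no such condition, and no text ranks the rows.

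There are also safeguards. The listed events go on the AE CRF with grade and relationship, hospital admission triggers an SAE form, a dedicated CRF feeds the model, the TMG may over-rule the model, and the SRC reviews DLTs. These keep the data recoverable. None of them says which rule to apply.

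Two limits are sound. Fatigue is also an expected radiotherapy effect (14.4.1), and 9.3.2 says that nearly all instances of the common toxicities arose with chemotherapy, so attribution will often be in question in A1 and the assumed rates there are weakly grounded. The simulated frequencies also depend on the assumed rate of other DLTs. With other-DLT rates of 0.12–0.22 (A1) and 0.15–0.25 (A2), 600 trials gave direct top-to-none shifts of about 0.5% and 1% at a 5% extra rate, 2% and 4% at 10%, and 19% and 15% at 20%.

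A reader might also count the row for ALT/AST elevation under 8 days as part of the conflict. It is not: it is the complement of the 8-day rule in 9.1.2. Nor is the mention in 9.3 of a non-DLT of grade 3 or higher contradictory in itself.

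**Conclusion.** The inconsistency is real. For a related grade 3 or worse event in seven listed classes, the protocol gives two scorings and no precedence. Section 9.1.2 appears to govern, but a site working from the later rows of 14.5 would not report the event as a DLT.

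The firmest measure of size is the first cohort, where one re-scored patient turns escalation into a hold in both A1 and A2. This rests on the SAP model and full follow-up, with no assumed event rate.

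A reader might infer that the same data will routinely give either the top schedule or no schedule. The documents do not support that. The full shift needs about 2 to 4 re-scored patients at a rate they do not state, and it is uncommon at 5% (at most 3% of trials in the table above). A reader might also take none as the trial stopping for toxicity, but it means only that no schedule is estimated at or below target. The point should be fixed; since 9.1.2 is already the cited definition and the events are recorded either way, it does not undermine the design.

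**What to change.** Reconcile 9.1.2 and 14.5 in one of two ways:

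- state that 9.1.2 governs DLT scoring and that the not-dose-limiting rows of 14.5 apply only to events that do not meet 9.1.2; or
- have the sponsor list in 9.1.2 any event classes and grades that it intends to exempt from the general grade 3 item. Which classes, if any, is the sponsor's clinical decision.

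Then align the DLT and SAE ticks throughout the 14.5 table, including the row for unlisted grade 3 or worse events. Before the next model run, re-score patients already treated under the single rule from the AE CRFs, which hold grade and relationship.

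The cost is a wording amendment to two sections and a one-off re-score of data already held. No new data collection or change to the model is needed.

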14.6 Suspected Unexpected Serious Adverse Drug Reactions (SUSARs)

All SUSARs must be reported by the Trial Office to the responsible Authority and REC within the required timelines:

- Fatal or life threatening SUSARs will be reported within 7 days of the Trial Office receiving the initial report. Any additional information will be reported within eight days of sending the first report.
- All other SUSARs will be reported within 15 days of the Trial Office receiving the initial report

In addition, other safety issues qualify for expedited reporting where they might materially alter the current risk assessment of an IMP or be sufficient to change IMP administration or the overall conduct of the trial. Chemotherapy SUSARs will be reported via the Yellow Card Scheme.

14.7 Expedited reporting of SAEs

The following SAE reporting requirements apply regardless of the Investigator's assessment of the causality or expectedness of the SAE. All SAEs should be reported on the trial SAE report form (see SAE report form and completion guidelines).

If a Serious Adverse Event occurs that requires reporting, a Serious Adverse Event reporting form should be completed and **scanned and emailed as a PDF attachment** within 24 hours of becoming aware of the event to:

Pharmacovigilance Office, OCTO

Email: [contact]

[contact]

If the SAE has not been reported within the specified timeframe, a reason for lateness must be provided when sending the SAE Report Form.

Investigators should also adhere to their local Trust policy for incident and SAE reporting in research. AEs which are serious must be reported to the Trial Office from the first dose of study medication up to and including 30 days after administration of the last dose of study treatment, or the end of the DLT reporting period, whichever is longer. Any SAE that occurs at any time after completion of treatment or after the designated follow-up period that the Investigator and/or Sub-Investigator consider to be related to any study drug must be reported to the Trial Office.

The Trial Office will be responsible for reporting all SAEs to MERCK KGAA, DARMSTADT GERMANY within 24 hours of receiving an SAE report.

14.8 Follow-up of Serious Adverse Events

A follow-up report must be completed when the SAE resolves, is unlikely to change, or when additional information becomes available. If the SAE is a suspected SUSAR then follow up information must be provided as requested by the Trial Office.

If new or amended information on a reported SAE becomes available, the Investigator should report this on a new SAE form using the completion guidelines. If using the original form to notify further information, you must initial and date all new or amended information so that all changes are clearly identified.

SAEs that are considered to be definitely unrelated to the trial intervention will not be followed up and monitored.

14.9 Reporting Adverse Events on the CRF

All AEs, including Serious AEs must be recorded on the case report forms (CRF) for that patient (unless otherwise specified in section 14.10). The information provided will include date of onset, event diagnosis (if known) or sign/symptom, severity, time course, duration and outcome and relationship of the AE to study drug. Any concomitant medications or any other therapy used to treat the event must be listed. The Investigator will provide an “other” cause for serious AEs considered to be unrelated to the study drug. Sites should ensure data entered into the CRF is consistent with the SAE report information where applicable.

Each separate AE episode must be recorded. For example, if an AE resolves completely or resolves to baseline and then recurs or worsens again, this must be recorded as a separate AE. For AEs to be considered intermittent, the events must be of similar nature and severity.

AEs occurring from the first dose of study medication up to the end of study visit must be recorded on the CRF. AEs may be spontaneously reported by the patient and/or in response to an open question from study personnel or revealed by observation, physical examination, or other diagnostic procedures. Any clinically relevant deterioration in laboratory assessments or other clinical finding is considered an AE. AEs which result in early withdrawal must be reported using the Early Withdrawal Form.

Terms and Grading of Events

All adverse events and toxicities must be graded according to the NCI Common Terminology Criteria for adverse events (NCI-CTCAE) Version 4.0 (currently up to Version 4.03).

